6.4 Sites

Recruitment will take place at 100 dermatological practices and ambulant clinics that are a) partially selected at random and b) accordant with the centers of AtopicHealth1. Due to the experience in AtopicHealth1 an active participation rate of 15% can be expected. Therefore, 700 practices need to be contacted.

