Study protocol

Health care characteristics and quality of care for atopic dermatitis in Germany

Principal investigator:

Univ.-[name]. [name] Director, Institute for Health Services Research in Dermatology and Nursing (IVDP) University Medical Center Hamburg-Eppendorf (UKE) [name], Germany

In cooperation with:

[name]. [name] University Hospital, Technical University Dresden

German Center for Health Services Research in Dermatology

Institute for Health Services Research in Dermatology and Nursing (IVDP) University Medical Center Hamburg-Eppendorf (UKE) [name] E-Mail: [contact] [contact], Fax: [name]

1 Synopsis

Study title	"AtopicHealth2" - Health care characteristics and quality of care		
	for atopic dermatitis in Germany		
Condition	Atopic dermatitis		
Objective	Generating routine data on quality of care, treatments needs, and guideline- compliant care for atopic dermatitis from the patient's and the physician's perspective		
Design	Non-interventional, multi-center, cross-sectional health care study in patients with atopic dermatitis under medical care		
Estimated number of participants	N = 1,500 adult patients with atopic dermatitis in medical care		
Inclusion criteria	 Diagnosed atopic dermatitis Patient understands the survey and is expected to be able to complete the questionnaire Patient gives written consent on participation Patient has signed the data protection declaration 		
Exclusion criteria	Lack of mental, physical or linguistic ability to participate in a questionnaire survey		
Main Outcomes	1. Severity levels		
	2. Health care situation and quality of care		
	3. Patient benefit of the ongoing therapy and compliance		
	4. Health economic outcomes		
Study duration	Appr. 100 weeks		
Observation period	One visit (cross-sectional study)		
Work packages	The following study periods are planned (some periods may be overlapping): Study preparation (incl. obtainment of ethics vote): 10 to 16 weeks Center recruitments: 8 weeks First patient inclusion: tbd Last patient inclusion: tbd Overall recruitment period: 52 weeks Final data management period: 4-12 weeks after last patient out Determination of assessed cost parameters: 4-8 weeks Data analysis: 4-8 weeks Final report: 4 weeks		
Statistical analysis	All data will be analysed with descriptive statistics and specified in terms of statistical standard values. Further statistical analyses will be performed		

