5.2 Goal and benefit of the study

The aim of the present planned study "AtopicHealth2" is the generation of up-to-date scientific data concerning the quality of care for atopic dermatitis in Germany. A particular focus lies upon the description of ongoing therapies, quality of life and individual treatment needs and benefits from the patient's perspective. Adult patients with all levels of severity and age groups are included. The Study is methodologically and contend-relatedly tied to the first national health care evaluation study AtopicHealth1. With these data, concerns about care from the patient-side as well as supply gaps can be characterized further and measures can be reached on different levels.

The planned study represents an outstanding occurrence in German health services research, as it is a continuation of the study AtopicHealth1, conducted in 2010, capturing the standard of care for atopic dermatitis from the patient's perspective with representative data, allowing comparisons over a period of more than 6 years. The results of the study intend to serve the scientific analysis of the current supply of care with topical therapy and systemic drugs and are applicable in the argumentation towards prescribers, users, cost bearers and decision-makers in health care policy ("health economic positioning"). Furthermore, the data serves acquiring knowledge regarding the preferences and application behavior of patients with atopic dermatitis. Multiple usage of the generated data is strived at.

Thus the study shows several significant benefits for the patients and supplying physicians:

- 1. The nationwide survey concerning the subjective burden of disease allows assessment of patient "distress" and the need for care concerning atopic dermatitis.
- 2. As an inventory control of the current care, the study enables an acquisition of the existing supply gap with solid data.
- 3. Due to profiling of the "poorly cared-for patient" and his or her needs, the study facilitates future care provision planning.
- 4. The recorded predictors of "poor care" are requirements for the targeted dismantling of "care barriers" to date, a not yet introduced strategy in Germany.
- 5. Due to the acquisition of quality indicators and benefit assessment from the patient's perspective, the study allows a profound analysis of the benefit as perceived by the patient of the hitherto appointed types of therapy.

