6.2 Objectives

Concerning the current study, the following questions will be clarified:

- How high is the subjective burden of disease of patients with atopic dermatitis in 2016/2017 in Germany?
- 2. What are the patient-specific needs in the course of medical care?
- 3. How is the quality of care for different levels of severity and therapeutic groups of the disease?
- 4. What kind of quality does the care measured via guideline compliant quality indicators and single items demonstrate compared to 2010?
- 5. How is the benefit of the medical services assessed from the patient's perspective?
- 6. To what extent are restrictions of compliance perceived from the patient's perspective and how are these explained?
- 7. To what extent is there an undersupply, particularly regarding treatment with systemic drugs?
- 8. Which predictors can be found for a proficient/poor care for atopic dermatitis patients?
- 9. How high are the costs-of-illness caused by atopic dermatitis and which predictors can be found?
- 10. Which impact does atopic dermatitis have on workability?

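### Patients enter only through dermatology sites, but the synopsis, aims and objectives on burden, undersupply, cost and work are worded for a wider population

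*Protocol*

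**What the plan says.** **Who can enter.** Section 6.4: "Recruitment will take place at 100 dermatological practices and ambulant clinics". Section 6.12 confirms that a patient is included only after giving written consent to the treating dermatologist. The inclusion criteria in 6.3.2 ask for adult age, the diagnosis, ability to answer the questionnaire and the two signatures. They do not mention dermatological care, so the list of sites alone sets the population. Section 6.3.1 adds that about 50 of about 100 sites enrol all severities and the rest enrol severe disease only.

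**Who the study is said to describe.**
- Synopsis, design row: "cross-sectional health care study in patients with atopic dermatitis under medical care". Participants row: "N = 1,500 adult patients with atopic dermatitis in medical care".
- Section 6.2, objective 1: "How high is the subjective burden of disease of patients with atopic dermatitis in 2016/2017 in Germany".
- Objective 7: "To what extent is there an undersupply, particularly regarding treatment with systemic drugs".
- Objective 9: "How high are the costs-of-illness caused by atopic dermatitis and which predictors can be found".
- Objective 10, on workability, likewise names no care setting.
- Section 5.2 describes the study as "capturing the standard of care for atopic dermatitis from the patient's perspective with representative data", calls the burden survey nationwide, and says that "the study enables an acquisition of the existing supply gap with solid data". It names cost bearers and health policy decision-makers among the intended audience.

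Table 1 in section 5.1 labels the 2010 predecessor as a study of patients in dermatological care and lists studies of insured persons and of the general population as separate target groups.

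**The concern.** The sampling frame and the stated target differ, and nothing in the protocol bridges them by restriction, weighting or linkage to other data. This matters most for undersupply: everyone enrolled has already reached a dermatologist, so one possible form of undersupply is absent from the sample by construction. For burden, cost and work impairment, people who attend a specialist may differ systematically from others with the diagnosis. Section 5.2 intends the results for use in policy argument, where a figure described as representative would readily be read as applying to all adults with atopic dermatitis in Germany.

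**Working it through.** The plan states no figure on this point, so there is none to reproduce. The check sets the passages side by side and then asks whether a direction of bias can be inferred.

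**1. Nested populations.**
- A: adults with the diagnosis in Germany (the natural reading of objective 1; nothing in objectives 7, 9 and 10 is narrower).
- B: adults with the diagnosis in medical care (synopsis).
- C: adults with the diagnosis attending a dermatological practice or clinic (6.4 and 6.12).

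C lies within B, and B within A. Only C can be sampled. Calling the data representative, without qualification, claims A or B.

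**2. Undersupply.** Let c be the share of the target population in dermatological care, and let u_in and u_out be the undersupply rates inside and outside it. Then

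population rate = c × u_in + (1 − c) × u_out,

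and the bias of the sample figure is u_in minus that rate. The protocol gives none of these inputs. Purely as an assumption, take u_in = 30% and c = 0.5:

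| u_out (assumed) | population rate | bias of sample figure |
|---|---|---|
| 80% | 0.5×30 + 0.5×80 = 55% | −25 points |
| 50% | 0.5×30 + 0.5×50 = 40% | −10 points |
| 30% | 30% | 0 |
| 10% | 0.5×30 + 0.5×10 = 20% | +10 points |

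Varying c from 0.3 to 0.9 and u_out from 5% to 80%, the bias runs from −35 points (c = 0.3: 30 − 65) to +17.5 points (c = 0.3: 30 − 12.5). Its sign depends entirely on u_out, which is unknown.

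**3. Mean burden or cost.** With r the ratio of the mean outside dermatology to the mean inside, the sample mean exceeds the population mean by the factor 1/(c + (1 − c) × r). With r assumed between 0.8 and 0.2:
- c = 0.3: 1/0.86 = 1.16 to 1/0.44 = 2.27
- c = 0.5: 1/0.90 = 1.11 to 1/0.60 = 1.67
- c = 0.9: 1/0.98 = 1.02 to 1/0.92 = 1.09

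If r were 1.2, the factor would fall below 1 (0.88 at c = 0.3, 0.98 at c = 0.9). A value of r below 1 is plausible for specialist attenders, but the protocol does not document it.

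**4. Sites restricted to severe disease.** Assume equal recruitment per site and a severe share s of 10% to 30% at the all-severity sites. The pooled severe share is then 0.5 + 0.5 × s, that is 55% to 65%. This raises pooled burden and cost. It could also raise a per-patient rate of undersupply with systemic drugs, which works against any understatement.

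**The case against.** The strongest reply is that the frame is disclosed. The synopsis already limits the study to patients under medical care, so adults treated by nobody are outside the declared study population. Section 5.2 ties the methods to the 2010 study, which the introduction places in dermatological practices, and keeping that setting supports the comparison with 2010 in objective 4. Objectives 2 to 6 and 8 concern needs, care received, benefit, compliance and predictors, and can properly be asked of attending patients. All of this stands. It narrows the synopsis problem to medical care versus dermatological care, but it leaves the wording of 5.2 and of objectives 1, 7, 9 and 10 untouched.

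Two stronger readings are tempting and are not supported.
- A reader might infer that undersupply will be understated. Objective 7 stresses systemic drugs, and patients outside dermatology may be milder and need them less often. Section 6.5 also leaves the definitions of high need and underprovision to be refined, so the protocol does not say whether access to a dermatologist counts as part of undersupply.
- A reader might infer that national cost totals will be wrong. Nowhere does the protocol plan to multiply per-patient cost by prevalence or to report such a total.

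**Conclusion.** The point holds as a mismatch between the sampling frame and the population claimed. The sample cannot represent adults treated outside dermatology, and undersupply due to not reaching a dermatologist cannot be seen in it. Both statements follow from the text and need no assumption. That per-patient burden and cost exceed those of all adults with the diagnosis is plausible, on the assumption that specialist attenders are more severely affected; the severe-only sites act in the same direction. For systemic-drug undersupply the direction is uncertain. The ranges in the working rest on assumed inputs and show only that the sign is open for undersupply and that the error could be material; they are not estimates for this study. The defect limits what may be concluded and does not invalidate the data collection.

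**What to change.** - In the synopsis, section 5.2 and section 6.2 (objectives 1, 7, 9 and 10), restate the target population as adults with atopic dermatitis attending dermatological practices or outpatient clinics.
- In 5.2, limit the claims of representativeness and of measuring the supply gap to that population.
- State that the undersupply result excludes lack of access to a dermatologist.
- State that burden and cost results are not to be carried over to all adults with the diagnosis.

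The cost is a few sentences and a narrower policy claim. Sites, recruitment and data collection do not change.

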6.3 Patients

6.3.1 Number of patients

The study will include 1,500 up to 2,000 adult patients, to be recruited by about 100 active sites. Approximately 50 sites are required to include patients with all levels of severity. The remaining sites should only include patients with severe atopic dermatitis.

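### With 15% of contacted practices expected to be active, and part of the sites carried over from AtopicHealth1, the design does not support calling the level estimates representative

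*Protocol*

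**What the plan says.** Protocol 6.4 (Sites) plans recruitment at "100 dermatological practices and ambulant clinics that are a) partially selected at random and b) accordant with the centers of AtopicHealth1". It continues: "Due to the experience in AtopicHealth1 an active participation rate of 15% can be expected. Therefore, 700 practices need to be contacted". Section 6.3.1 gives the matching target: "1,500 up to 2,000 adult patients, to be recruited by about 100 active sites".

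Section 5.2 (Goal and benefit of the study) describes the study as "capturing the standard of care for atopic dermatitis from the patient's perspective with representative data, allowing comparisons over a period of more than 6 years". Its list of benefits opens with "The nationwide survey concerning the subjective burden of disease", and it expects to document gaps in supply for use with cost bearers and policy makers.

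Section 6.2 asks for levels: burden (objective 1), quality of care (3), patient-assessed benefit (5), extent of undersupply (7) and cost of illness (9). It also asks for comparisons: with 2010 (4), between severity and therapy groups (within 3), and for predictors (8, and part of 9).

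Sections 6.7 to 6.10 cover power, data entry, descriptive and inferential analysis, and quality assurance. None of them mentions practices that are contacted but do not become active.

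**The concern.** A random draw of practices gives a random sample only if most of those drawn take part. Here about six in seven contacted practices are expected not to be active. The centres carried over from AtopicHealth1 had already chosen to take part in 2010.

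Interest in atopic dermatitis could plausibly influence both whether a practice joins and how it scores. Several process indicators in Table 2 (diagnostic criteria assessed, RAST testing, individual counselling) reflect what a practice does. Section 5 itself names hesitant prescribing by some dermatologists as a possible cause of undersupply, so variation between prescribers is part of the study's premise.

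At stake is what the level estimates describe: care in Germany, or care at the sites that joined. Section 6.7 relies on n = 1,500, which controls sampling error but not selection. Facts about practices that do not join are best recorded at contact and may be lost once recruitment closes.

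**Working it through.** **1. The plan's own figure.** Inputs from 6.4: 100 sites, 15% active participation.
- Contacts needed = 100 / 0.15 = 666.7, so 667, rounded up to 700.
- Check: 700 × 0.15 = 105 active sites, leaving 700 − 105 = 595 (85%) not active.
- If exactly 100 are active, participation is 100/700 = 14.3%.

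The figure of 700 stands.

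**2. Sampling error, for scale.** Inputs: 13.3% of patients rating their care as poor or deficient in AtopicHealth1 (section 5), n = 1,500.
- 95% half-width = 1.96 × √(0.133 × 0.867 / 1500) = 1.72 percentage points, under simple random sampling.
- With 1,500/100 = 15 patients per site and an assumed intraclass correlation of 0.05, the design effect is 1 + 14 × 0.05 = 1.7 and the half-width is 1.72 × √1.7 = 2.24 points.

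**3. Selection bias of a level.** Let s be the share of the patients concerned who are treated in active practices, and d the gap in the level between active and non-active practices. Then the bias is (1 − s) × d in size. The protocol gives neither s nor d. The 15% is a share of practices, and s equals it only if active and other practices treat similar numbers of these patients. All values of s and d below are assumptions.

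| Assumed gap d | Bias if s = 15% | Bias if s = 30% |
|---|---|---|
| 2 points | 0.85 × 2 = 1.7 | 0.70 × 2 = 1.4 |
| 5 points | 0.85 × 5 = 4.25 | 0.70 × 5 = 3.5 |
| 10 points | 0.85 × 10 = 8.5 | 0.70 × 10 = 7.0 |

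**4. Gap at which bias equals the half-width.**
- Simple random sampling: 1.72 / 0.85 = 2.0 points (s = 15%); 1.72 / 0.70 = 2.5 points (s = 30%).
- Design effect 1.7: 2.24 / 0.85 = 2.6 points; 2.24 / 0.70 = 3.2 points.

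The sample size does not appear in the bias formula, so recruiting 2,000 patients instead of 1,500 would leave the bias unchanged.

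**The case against.** The strongest reply is that nothing in the protocol shows non-active practices to differ at all. That is correct. A reader might infer that quality is overstated and undersupply understated by several points, but the documents give no data on non-participants, so existence, direction and size are all unknown.

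Other parts of the reply also stand:
- It is tempting to multiply any gap by 0.85. That figure counts practices, while the outcomes are measured on patients. The rate is also for *active* participation, so the 85% may include practices that agree but enrol nobody.
- The 13.3% example concerns care over recent years and may include care received elsewhere. It only sets a scale.
- A shift common to both surveys or to all subgroups need not carry over in full to comparisons, and reusing AtopicHealth1 centres supports continuity with 2010. The protocol does not show that selection worked alike in both surveys, so the most that can be said is that comparisons may be less affected.
- Weighting to the contact list might seem to restore representativeness. It would not. The list mixes a random draw with AtopicHealth1 centres and counts practices, not patients. Crossing 16 federal states with three two-way facts gives 16 × 2 × 2 × 2 = 128 cells for about 105 sites.

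One could add that such matters belong in the SAP, which was not available. That holds for weighting. It does not hold for the claim in 5.2, which this protocol makes, or for information on contacted practices, which has to be planned before recruitment.

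**Conclusion.** The point holds as a mismatch between claim and design. Section 5.2 uses a word that the recruitment in 6.4 cannot support for the level estimates, and no other section supplies the support. The finding rests on the expected 15% rate and the mixed origin of the sites, both stated in the protocol.

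The numbers illustrate sensitivity and are not an estimate of bias. Under the assumptions in the working, a gap of about 2 to 3 points between active and non-active practices is enough for selection to match the whole sampling margin of a 13.3% level.

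The documents do not support saying that the results are biased in a known direction, that the figure of 700 is wrong, or that the comparison with 2010 is invalid. The restriction of some sites to severe patients in 6.3.1 is a separate matter, and this point does not depend on it.

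**What to change.** 1. **Section 6.4.** Keep a log of all contacted practices with facts known at contact: region, urban or rural, practice or clinic, random draw or AtopicHealth1 centre. Report active against non-active practices on these facts, and show results separately for randomly drawn sites and AtopicHealth1 centres.
2. **Section 5.2.** Replace the reference to representative data by *data from participating dermatological sites*, and state practice self-selection as a limit on the level estimates.

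Optionally, add a short reply form for practices that decline. It will have non-response of its own and can only supplement the log. Any weighting belongs in the SAP as a sensitivity analysis and does not by itself justify the stronger word.

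The cost is minor record-keeping during site recruitment and a less favourable claim in 5.2. Site numbers, sample size and patient procedures do not change.

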6.5 Project development

The project consists of the following steps:

- 1. Conception
 - a. Information to the boards of the German dermatology societies DDG and BVDD
 - b. Cooperation agreements
 - c. Obtainment of ethics vote
- 2. Planning
 - a. Systematic literature research on national and international standards on diagnosis and treatment of atopic dermatitis following Cochrane criteria
 - b. Refinement of definitions for core concepts of outcomes, e.g. quality of care, status of "high need" and status of "underprovision of health".
 - c. Application of quality of care indicators that were developed based on "AtopicHealth1" by an expert committee consisting of 10 members:
 - i. Process indicators (derived from expert consensus based on guideline)
 - ii. Outcomes indicators (derived from expert consensus process)
 - d. Biometric planning
 - e. Adaptation and final versions of study forms and questionnaires
- 3. Study conductance
 - a. Recruitment of centres
 - b. Data collection in the centres
 - c. Data entry and -management
 - d. Determination of assessed cost parameters
- 4. Data analysis and statistical evaluation
- 5. Final report
- 6. Publications

6.6 Outcomes

If obtainable from patient details, the outcome-parameters are selected, if possible, in a large consensus with the international standards as well as the preliminary publications of the HOME-Initiative (Schmitt J et al. and Augustin M et al). The following target parameters are intended:

1) Description of the level of severity

- Clinical: SCORAD (Darsow et al. 2005), Body Surface Area (grid for recording) (Wallace 1951); optionally EASI (to be discussed with sponsor)
- Dermatology Quality of Life: DLQI (Finlay und Khan 1994), EQ VAS (generic health questionnaire); (EuroQol--a new facility for the measurement of health-related quality of life 1990; Schulenburg vd et al. 1998)

2) Description of the health care situation and quality of care

- Process: quality: "Health care-index" from 12 indicators of process quality (see below, 6.6.1)
- Outcomes: quality: based on a selected number of single outcomes, e.g. DLQI, PBI, SCORAD
- Data regarding the present supply chain

3) Presentation of patient benefit of the ongoing therapy and compliance

- Patient benefit Index PBI (Augustin et al. 2009; Blome et al. 2009)
- Compliance Scales (adapted from AtopicHealth1)

4.) Health economic outcomes

- Direct costs (treatment costs, out-of-pocket costs): EKK (adapted from "PsoHealth3")
- Indirect costs incl. workability: EKK (adapted from PsoHealth3)
- Presenteism and absenteeism: Work Productivity and Activity Impairment (WPAI) (Reilly et al. 1993)

